13.3 Unexpected Adverse Event

An unexpected adverse event is defined as an event that has a nature or severity, or frequency that is not consistent with the applicable investigator brochure, or the prior medical condition of the subject or other treatment given to the subject.

"Unexpected," as used in this definition, refers to an adverse drug experience that has not been previously observed and reported in preclinical or clinical studies rather than an experience that has not been anticipated based on the pharmacological properties of the study drug.

13.4 Monitoring and Recording Adverse Events

All AEs will be assessed by the investigator or qualified designee and recorded in the source documentation. The investigator should attempt to establish a diagnosis of the event on the basis of signs, symptoms and/or other clinical information. In such cases, the diagnosis should be documented as the adverse event and/or serious adverse event and not described as the individual signs or symptoms. The following information should be recorded:

- Description of the adverse event using concise medical terminology
- Description as to whether or not the adverse event is serious, noting all criteria that apply
- The start date (date of adverse event onset)
- The stop date (date of adverse event resolution)
- The severity (grade) of the adverse event
- A description of the potential relatedness of the adverse event to study drug, a study procedure, or other causality
- The action taken due to the adverse event
- The outcome of the adverse event

Because adverse events are not expected for this IP, and have not been seen in our experience with FES, patients with AEs possibly related to the IP will be discontinued. The principal investigator will exercise their discretion in determining the attribution of AEs.

Patients who discontinue the study will be asked if follow-up via telephone is acceptable. If they agree to receive communication from us, we will follow-up with them 30 days following administration of the IP. If any unexpected risks are discovered which may affect patients more than 30 days following administration, all previous participants will be informed.

13.5 Grading Adverse Event Severity

All AEs will be graded in severity according to the NCI Common Terminology Criteria for Adverse Events (CTCAE) Version 4.0. If a CTCAE criterion does not exist, the investigator should use the grade or adjectives: Grade 1 (mild), Grade 2 (moderate), Grade 3 (severe), Grade 4 (life-threatening), or Grade 5 (fatal) to describe the maximum intensity of the adverse event.

13.6 Attribution of an Adverse Event

Association or relatedness to the study agent will be assessed by the investigator as follows:

- Definite: The event follows a reasonable temporal sequence from exposure to the investigational agent, has been previously described in association with the investigational agent, and cannot reasonably be attributed to other factors such as the subject's clinical state, other therapeutic interventions or concomitant medications; AND the event disappears or improves with withdrawal of the investigational agent and/or reappears on re-exposure (e.g., in the event of an infusion reaction).
- Probable: The event follows a reasonable temporal sequence from exposure to the investigational agent and has been previously been described in association with the investigational agent OR cannot reasonably be attributed to other factors such as the subject's clinical state, other therapeutic interventions or concomitant medications.
- Possible: The event follows a reasonable temporal sequence from exposure to the investigational agent, but could be attributable to other factors such as the subject's clinical state, other therapeutic interventions or concomitant medications.
- Unlikely: Toxicity is doubtfully related to the investigational agent(s). The event may be attributable to other factors such as the subject's clinical state, other therapeutic interventions or concomitant medications.
- Unrelated: The event is clearly related to other factors such as the subject's clinical state, other therapeutic interventions or concomitant medications.

For general AE assessment, an AE is considered related if it is assessed as definitely, probably, or possibly related; unrelated if it is assessed as unlikely related or unrelated.

13.7 Adverse Event Recording Period

AEs will be monitored and recorded in study-specific case report forms (CRFs) from the time of first exposure to an investigational product in this study. Patients will be contacted 24 hours following IP administration to evaluate for signs of AEs. AEs with an onset date prior to the first exposure to an investigational product will not be recorded, except in the case of clinically significant worsening of the AE during the specified AE monitoring time frame.

13.8 Adverse Event Reporting Requirements

Expedited AE reporting for this study will be completed with the FDA and as required by FDA MedWatch, and the IND sponsor. These requirements are briefly outlined in the table below.

All life-threatening adverse reactions reports are submitted to the sponsor, and to all participating investigators. The sponsor will report all attributable, unexpected life-threatening or otherwise serious AEs to the FDA. A copy of the report is kept on file. If a new risk is identified to be attributable to FES, it will also be reported to the IRB as a protocol and consent change within 10 days.

Table 13.2 Reporting Requirements

	Unexpected		Expected
	Adverse Reaction (known or suspected attributable to the use of [¹⁸ F]FES)	AE not attributable to [¹⁸ F]FES	AE, AR
	Serious including life-threatening (or death)	Nonserious	Life-Threatening or serious or not serious
Reporting Time Requirement to the FDA	Sponsor report to FDA ASAP and within 7 days of discovery of event	Annual Continuation Review submission	Annual Continuation Review submission
Reporting Form for the FDA	IND Safety report of potentially serious risk	Annual Reports / Case reports	Annual Reports / Case reports
Reporting Time Requirement to the local IRB	Report to IRB ASAP within 10 days of discovery of event (suspected is defined as 50% probability attributable to [¹⁸ F]FES study) this also includes any increased risks with the study even without an AE	At continuation review time	At continuation review time
Reporting form for the IRB	Expedited Reporting Form for Unanticipated Problems or Noncompliance and Adverse Event Reporting Form	Form for Unanticipated Problems or Noncompliance, Case reports on continuation form, Data Safety Monitoring Reports	Form for Unanticipated Problems or Noncompliance, Case reports on continuation form, Data Safety Monitoring Reports

14.0 CRITERIA FOR ENDPOINT EVALUATIONS

For the purposes of this study, the outcome measured will be the change in FES and FDG PET measures between the serial sets of scans. Response evaluations will not be evaluated as part of this study, though the information may be recorded if it is collected for treatment studies the patient may be participating. Patients may also be followed for up to 20 years for disease progression and overall survival.

The FES PET scan will be assessed with:

- Qualitative FES uptake: all known disease sites positive vs. heterogeneous or absent FES uptake.
- Quantitative FES uptake: SUVs in all lesions measured at baseline and repeat scan (and at third scan if indicated)
- Quantitative change in FES uptake: percentage and SUV unit change in SUV between baseline and repeat FES PET scan

Qualitative Visual Assessment

Qualitative (visual) assessment of level of uptake in sites of recurrent breast cancer is performed for all studies. In this analysis, trained observers determine whether FES uptake is present above background at sites of breast cancer. Active disease sites are identified by the FDG PET scan performed close to the time of FES PET, in conjunction with conventional imaging such as CT, MRI, and bone scan. Active sites of disease are defined as sites with (1) abnormal uptake on FDG PET and (2) either biopsy confirmation or unequivocal correlative findings on at least one other modality. For each site of active disease, two trained observers blinded to the clinical data, but with any available FDG PET and correlative imaging, will determine whether FES above background levels is present or absent. Differences between observers will be resolved by consensus.

Quantitative Assessment

FES static survey images will undergo region of interest (ROI) analysis as follows: Lesion location will be identified using FES scans along with FDG scans with reference to CT or ultrasound. All patients will have undergone clinically motivated FDG PET scans for staging prior to FES imaging. CT, MRI, ultrasound or bone scan will be available on all patients with suspected metastatic disease. Although FES and FDG imaging will be performed on separate days, studies will be performed with the patient in the same position and images will be co-registered using common anatomic landmarks such as the lung outline, cardiac blood pool, liver contour, and body outline. In this way, regions can be drawn on the FDG images and transferred to the FES images for quantitative analysis which is important in identifying tumor locations, especially in ER-negative tumors which are not visualized on FES imaging. For each disease site, a set of 1.5 cm diameter regions on three adjacent planes with the highest lesion FES uptake will be drawn to determine maximal FES uptake. Up to the 10 largest sites seen on the static torso survey will be quantified. Partial-volume correction will not be used because only sites 1.5 cm or greater diameter will be included in quantitative analysis.

FES uptake will be quantified using the standard uptake value (SUV, defined below). For each site, we will record the average and maximum SUV within the ROI set for each site of disease.

For each subject, we will calculate the average and range of FES uptake values for active disease sites. The FES uptake will be compared with subsequent response to endocrine therapy and TTP.

FDG studies will also be quantified for uptake in a similar fashion. On FDG studies, simple SUVs will be generated using the average tissue activity over the imaging period, which are typically 45 and 75 minutes after injection. We will record the maximum FDG SUV for each site of disease. Uptake at tumor sites using the standardized uptake value (SUV) is calculated as:

$$SUV = \frac{\overline{C}_t}{ID / wt}$$

where \overline{C}_t is the average tumor uptake after injection for the period of the static imaging for torso surveys (MBq/mL), ID is the injected dose (GBq) and wt is the patient's weight (kg). Note that either standard or metric units can be used to calculate SUV as long as only one type of unit is used for each calculation.

Biologic Correlates

Optional blood sample may be collected at the time of the FES PET scan procedure for determination of serum hormone levels (estradiol, estrone, follicle-stimulating hormone, sex hormone binding globulin, testosterone, free testosterone) and liquid biopsy.

Patients participating in this study will have undergone clinical biopsy of the primary tumor and/or metastasis for which ER, PgR, and HER2 expression will be determined by IHC. Clinical records of these assays will be reviewed, and the assays themselves may be reviewed as needed.

On patients for whom archival biopsy material can be obtained, additional assays may be performed, and may include repeat and standardized ER, PR, and HER2 assays.

Patients with metastatic or recurrent disease may consent to optional research biopsies of the tumor performed at the baseline, i.e. prior to start of the selected endocrine targeted therapy, and after 1-12 weeks on therapy. Obtained tissues will be analyzed

for a baseline expression and post-therapy changes in protein and genomic expression including ER, PgR, and HER2, using IHC methods and PI3K and ESR1 using Oncoplex. Some samples will be assayed for intra-tumor steroid hormone levels (estradiol, estrone, testosterone, dihydrotestosterone) using IHC and/or mass spectrometry techniques.

In some patients undergoing biopsy, a whole blood sample will be drawn during the same time point to allow correlation of steroid hormone levels in serum with levels in biopsy tissue.

Assays for ER and PgR will be read using the Allred scoring system, which provides a semi-quantitative and qualitative assessment of tumor expression levels (Harvey, 1999). IHC is the primary assay methodology for HER2. Scoring of HER2 is done by assessing intensity of the membranous stain (0, 1+, 2+, 3+). Scores of 0 and 1+ are considered negative and score of 3+ is considered positive. Score of 2+ is considered indeterminate and will be validated by fluorescence in situ hybridization (FISH) (HER-2 DNA probe kit; Abbott Molecular Inc., Des Plaines, IL)(Yaziji, 2004). Analysis of HER2 will be done using information from the IHC assays and the FISH confirmation when required.

Measurement of these tumor-associated indices may enhance the predictive value of PET FES, provide information to better understand mechanisms of resistance to endocrine therapy, and eventually determine which patients are likely to appreciate clinical benefit as a result of endocrine therapy, even in the absence of an objective response.

Time to progression (Progression-free survival): Time to progression (and progression-free survival) will be measured as the time from the start of endocrine therapy to the time the patient is first recorded as having disease progression. If a patient never progresses while being followed, the patient will be censored at the time he/she terminates follow-up or by date of disease progression or death.

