FDG PET and CT will be used as staging tests for this study and FDG will also serve as a comparator for tumor localization with the FES imaging. Patients will have a clinical FDG PET scan prior to the start of treatment as part of their standard care; their treating physician will order this. In rare cases where an FDG PET has recently been performed at an outside medical facility but the scan has inadequate image quality or insufficient quantitative information, or for patients who would not be ordered as a standard part of the patient's care, a baseline FDG scan will be done as part of this protocol. A second FDG PET scan will be done as a study procedure concurrent with the FES PET timing stipulated by treatment regimen (this may vary from 1 to 12 weeks post treatment start depending on regimen). In the subset of patients undergoing a third FES PET scan there may also be a research FDG PET done at the same time point if indicated by the treatment regimen.

After the FES and FDG baseline imaging (see schematic below), the patients will start or change therapy, typically within 30 days, and be followed clinically for up to 20 years. Lesion location will be identified using clinical FDG scans with reference to clinical CT for metastatic disease or ultrasound, mammography, and/or breast MRI for primary tumors in patients presenting with metastatic or recurrent disease that still have a primary breast lesion. FES and FDG images will be spatially co-registered and tumor regions will be drawn on the FDG images and transferred to the FES images for quantitative analysis of FES uptake in both ER positive and ER negative tumors. For FDG studies, SUVs will be generated.

[figure not shown]
The FES uptake from images will be analyzed qualitatively by visual assessment and quantitatively using a standard uptake value (SUV). Serial measurements of hormone levels in peripheral blood may be used with some treatment regimens to allow determination of efficacy of endocrine therapy. ER, PR and HER2 assays will allow determination of hormone receptor status and

whether HER2 over-expression indicates estrogen-independent growth in some treatment studies, however, there may not be pathologic correlates in all studies.

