8.1 Treatment Plan Overview

Figure 6.1 Outline (Schema) of the [18F]FES Study Protocol. a) FDG PET is not required for primary breast cancer patients unless required for localization or requested by treating physician. b) Where available and medically appropriate, a clinical or research biopsy that involved sampling of a relevant lesion within 6 months prior to the enrollment may be utilized in place of the baseline optional biopsy. c) Repeat FDG PET may be omitted in patients on SERD therapies.

Initial visits prior to [18F]FES PET: Patients who are identified as potential candidates for the [18F]FES PET study will be approached to explain the nature of the study and to obtain their written informed consent to be enrolled in the protocol. Heart rate and blood pressure will be recorded at the time of clinic visit where study is considered or at the time of consent. The patient will have a clinical FDG PET/CT scan if a recent FDG scan has not already been obtained. The FDG PET/CT scan should be obtained close to the time of FES PET/CT, typically within 14 days of the [18F]FES PET/CT scan. An additional FDG PET/CT scan may be done as a research scan if the patient has undergone a recent PET scan at an outside institution or if they are unable to obtain a clinical PET scan as part of their clinical care. The research FDG PET/CT scan in this instance will be identical in procedure to a clinical FDG scan. The following additional patient data will be obtained: histological diagnosis, age at radiologic diagnosis, weight, gender, ECOG score and other treatment modalities used. Correlative radiology including CT, MRI, or bone scan, and laboratory tests measuring renal, blood and liver function will also be collected, for values within 30 days of the FES PET/CT scan. For patients referred from outside the UW health system, patient records, and biopsy material and imaging as necessary, will be reviewed to determine eligibility for the study. Patients without a clinical evaluation in the last 30 days are unexpected; in these instances a clinical evaluation will be completed.

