17.0 STATISTICAL CONSIDERATIONS

Analysis Plan

The primary application will be pilot studies with enrollment of about 20 patients, in which the in vivo effects of endocrine-targeted therapy are measured by serial FES PET. The primary endpoints will be quantitative and qualitative measures of FES uptake, and measures of change in FES uptake between pre-therapy and post-therapy scans (Section 6.10.2). Additionally, patients will be followed for disease progression. Associations among FES and FDG PET measures, progression, and biological correlates (Section 6.10.3) may be examined in descriptive analyses.

An expected primary analysis is to examine whether FES uptake changed on average between serial assessments. This may be assessed by a one-sample test of the percent change in FES SUV. For example, a one-sided test at the 0.05 level of significance could evaluate whether the average percent change in FES SUV was greater than 20%, considered a biologically significant change. In serial FES SUV measurements of heavily-pretreated breast cancer patients, change in FES SUV was approximately normally distributed with a standard deviation of about 25 percentage points, for both patients treated with blocking therapy (tamoxifen or fulvestrant) or non-blocking therapy (aromatase inhibitor). Using this standard deviation and n=20 to test whether the average change was greater than 20%, the power would be 0.97 if the true change is 40%, and 0.85 if the true change is 35%. To conclude only that the average percentage change was different from zero (using a two-sided test at the 0.05 level of significance), power would be 0.95 to detect a true average change of 20% (and 0.85 if the true standard deviation were 30 percentage points).

Other analyses for pilot studies could examine what proportion of patients experienced a threshold in percentage change, or surpassed a targeted follow-up FES SUV value. These percentages will be reported using a 90% Wilson score binomial confidence interval. Width of these confidence intervals for pilot studies of n=20, n=25, and n=30 are given in Table 6.3 for a range of observed percentages.

Table 17.1: 90% Wilson score binomial confidence intervals (CIs) by percent observed and sample size.

observed percentage (CI) for n=20	observed percentage (CI) for n=25	observed percentage (CI) for n=30
0.1 (0.03, 0.26)	0.12 (0.05, 0.27)	0.1 (0.04, 0.23)
0.2 (0.09, 0.38)	0.20 (0.10, 0.36)	0.2 (0.11, 0.34)

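### Could the primary change in FES uptake end up comparing different lesions at baseline and at the repeat scan?

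*Combined protocol and SAP*

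**What the plan says.** Section 3.3.1 makes FES uptake, and its change from pre-therapy to post-therapy scan, the primary endpoint. Section 17.0 gives the expected analysis: "This may be assessed by a one-sample test of the percent change in FES SUV", with n=20 and a standard deviation of about 25 percentage points.

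Section 14.0 describes the measurement in three places:

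- The opening bullets list SUVs for lesions at the baseline and repeat scans, then the percentage and SUV-unit change between those two scans.
- Under Qualitative Visual Assessment: "Active disease sites are identified by the FDG PET scan performed close to the time of FES PET".
- Under Quantitative Assessment: "Lesion location will be identified using FES scans along with FDG scans with reference to CT or ultrasound"; "Up to the 10 largest sites seen on the static torso survey will be quantified"; "only sites 1.5 cm or greater diameter will be included in quantitative analysis"; and then "For each subject, we will calculate the average and range of FES uptake values for active disease sites". The next sentence relates FES uptake to later response and time to progression.

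On timing, Section 8.1 (Treatment Plan Overview) says of the baseline pair: "The FDG PET/CT scan should be obtained close to the time of FES PET/CT, typically within 14 days". Section 3.3 adds: "A second FDG PET scan will be done as a study procedure concurrent with the FES PET timing stipulated by treatment regimen". Sections 3.3 and 8.1 and Appendix A allow the repeat FDG to be left out for patients on SERD therapy.

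**The concern.** The Section 17.0 test needs one percent change per patient, and the only patient-level FES summary is the average over active sites. Three rules decide which sites enter that average: FDG activity, the ten-largest cap and the 1.5 cm limit. None is tied expressly to baseline. Because a second FDG accompanies the repeat FES, a literal reader could redraw the list on treatment. A site that had lost FDG uptake, shrunk below 1.5 cm or fallen out of the ten largest would then leave the follow-up average while staying in the baseline one.

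The percent change would then mix drug effect with a change of lesions, and two analysts could report different values for one patient. Section 6.1 requires only one site of 1.5 cm or more, so a patient with a single qualifying site could have no follow-up value. On SERDs without a repeat FDG, no passage names the images that supply the regions for the repeat FES.

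**Working it through.** **1. The plan's own figures.** Inputs from Section 17.0: n=20, SD 25 (also 30), 5% level. Standard error = 25/√20 = 5.59. Power by the normal approximation = Φ(difference/SE − z).

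| Test | Calculation | Result | Stated |
|---|---|---|---|
| One-sided against 20%, true 40% | Φ(20/5.59 − 1.645) | 0.973 | 0.97 |
| One-sided against 20%, true 35% | Φ(15/5.59 − 1.645) | 0.850 | 0.85 |
| Two-sided against 0, true 20% | Φ(20/5.59 − 1.960) | 0.947 | 0.95 |
| Same, SD 30 (SE 6.71) | Φ(20/6.71 − 1.960) | 0.846 | 0.85 |

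All four reproduce. None changes if one baseline lesion set is carried forward.

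**2. Which reading the text supports.**

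- Change has its own definition in the Section 14.0 bullets, next to lesion SUVs at both scans. Taken together, these favour paired lesions.
- The average over active sites is followed by a comparison with response and time to progression. The plan never names it as the input to the test of change.
- The FDG scan near the FES scan is mentioned in the singular, under the visual read. Section 8.1 uses the same phrase for the baseline pair. Reading it as a rule for each scan adds a word that is not there.
- Section 3.3 locates lesions on clinical FDG, and Section 14.0 says patients have a clinical staging FDG before FES imaging. The clinical FDG is the pre-treatment scan; the second is a study procedure.
- Section 14.0 transfers FDG-drawn regions to the FES images so that sites invisible on FES are still measured. Loss of FES signal alone therefore removes no site.

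**3. What a lost lesion would do.** Let B and F be the mean SUV over all k sites at baseline and repeat, and f the lost site's repeat SUV. The follow-up mean without that site is (kF − f)/(k − 1), so the percent change shifts by 100 × (F − f)/((k − 1)B) points. All SUVs below are assumed.

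- Example A: 4, 4, 4 becomes 1.0, 2.8, 2.8. B=4.0, F=2.2, change −45%. Losing the 1.0 site shifts this by 100 × 1.2/(2 × 4) = +15 points, to −30%.
- Example B: 6, 3, 3, each down 30%. B=4.0, F=2.8, change −30%. Losing the hottest site (f=4.2) shifts this by 100 × (−1.4)/(2 × 4) = −17.5 points, to −47.5%.

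The shift can go either way. If 2, 5 or 10 of 20 patients each moved 15 points in the same direction, the mean would move 15 × 2/20 = 1.5, 15 × 5/20 = 3.75 or 15 × 10/20 = 7.5 points, against the SE of 5.59. Such a shift needs several things at once: a redrawn list; loss of FDG uptake, shrinkage or a change in size rank by the repeat scan; a link between that loss and FES uptake; and the same direction across patients. The documents give no rate for any of these.

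**4. SERD patients without repeat FDG.** On the typical windows, the baseline FDG would be at most 14 + 84 = 98 days old at the repeat FES (Section 8.1 and Appendix A), or 14 + 30 + 84 = 128 days if the 30 days to start of therapy is added. The minimum is about 7 days. A list fixed at baseline uses that older scan by design. Its sites are found again by co-registration on anatomic landmarks, and the low-dose CT of the repeat FES PET/CT is also available.

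**The case for a change.** The best case for a change is that the authors knew how to write a same-site rule and did so for the repeat biopsy (Section 8.1 and Appendix A), but not for the scans that carry the primary endpoint. The bullet on lesion SUVs at baseline and repeat could mean lesions measured at both scans, or whatever was measured at each. Even strict pairing drops a lost lesion: in Example A the two remaining pairs still give 4.0 to 2.8, or −30%. The patient-level formula is also unnamed, and it matters. With assumed SUVs of 6, 3, 3 becoming 1.5, 2.7, 2.7, the mean falls from 4.0 to 2.3 (−42.5%), while the lesion changes of −75%, −10% and −10% average −31.7%. Section 14.0 records both the ROI average and the maximum without choosing between them.

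The silence is real, and so is the choice of formula. But these are working details of a pilot of up to 20 patients whose tests are worded as options and whose scans do not direct therapy. The biopsy rule shows that the authors think in terms of the same lesion; it is not evidence that they meant to change lesions between scans.

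The one step that goes beyond writing down the obvious is to keep lesions that have shrunk below 1.5 cm in the primary set. That cuts against the plan's reason for not using partial-volume correction, and it can exaggerate decline. Dropping them has its own cost, as Example A shows. Neither choice is plainly better.

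**Conclusion.** No change follows. The plan leaves three things unsaid: that baseline lesions are re-measured, where the regions come from when repeat FDG is omitted, and which patient-level formula and SUV metric apply. For the first two, Sections 3.3 and 14.0 point to the sensible answer: the same lesions, located from the baseline FDG. The third is ordinary detail for analysts to settle. How to treat lesions now below 1.5 cm is a fair trade-off.

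No stated figure is wrong, and the four powers stand. Shifts of 15 to 17.5 points in one patient, or 1.5 to 7.5 points in the cohort mean, appear only on assumed SUVs and on a scan-by-scan lesion list that the text does not state. The conclusion rests on the imaging team following the same lesions through serial scans. The wording supports that but does not prove it, and the documents cannot show how often lesions would otherwise be lost.
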